3.2 Evaluations

This clinical study will assess the primary and secondary evaluations as described below.

3.2.1 Primary Evaluations

Primary Safety Evaluation:

The primary safety evaluation is freedom from major adverse events and radial access complications within 30 days post-procedure.

Major Adverse Events are defined as:

1. Death
2. MI
3. Stroke

Radial Access related complications are defined as:

1. Radial artery occlusion
2. Hand ischemia
3. Arteriovenous fistula
4. Pseudoaneurysm
5. Any complication requiring surgical and/or endovascular intervention within 30 days of index procedure.

Primary Efficacy Evaluation:

The primary efficacy evaluations are procedural success and technical success.

1. Procedural success is defined as completing the planned procedure without femoral access bailout.
2. Technical success is defined as delivery of HydroPearl to the target vessel and slowing the blood flow with microsphere embolization. Embolization may be confirmed clinically or radiologically at the discretion of the site investigator.

3.2.2 Additional Evaluations

Additional evaluations include:

1. Incidence of Radial Artery Occlusion Complications at any time
 - a. Arteritis
 - b. Cellulitis
 - c. Ecchymosis
 - d. Pain at puncture site
 - e. Hematoma

2. Quality of Life and health economics
3. Post embolization syndrome
4. Procedural endpoints:
 - a. Blood loss
 - b. Patient radiation exposure
 - c. Contrast volume
 - d. Time to hemostasis
 - e. Total procedural time
 - f. Time to discharge
 - g. Operative time
5. Access endpoints:
 - a. Radial artery spasm,
 - b. Time to discharge
6. Closure endpoints
 - a. Time to hemostasis
 - b. Time to ambulation
7. Tumor type
8. Number and size of tumors / fibroids
9. Post embolization syndrome
10. UFE:
 - a. If post-op MRI is obtained per standard of care: Effectiveness of HydroPearl measured by MRI.
 - i. Infarction is characterized by complete (100%), 90-99%, 50-89%, or less than 50%.
 - ii. Uterine Volume
 - iii. Dominant Fibroid Volume
 - b. EQ-5D
 - c. UFS-QoL
 - d. Return to normal activities
 - e. Pain VAS
 - f. Symptoms including bleeding and bulk
 - g. Pregnancy intention and occurrence
11. PAE:
 - a. IPSS with Quality of Life

- b. EQ-5D
- c. Return to normal activities
- d. Pain VAS
- e. Qmax
- f. Prostate volume

12. Liver Tumor Embolization:

- a. Tumor response (mRECIST - CR, PR, SD, PD)
- b. EQ-5D
- c. Return to normal activities
- d. Pain VAS
- e. Disease stage

13. Other Hypervascular Tumors

- a. Infarction
- b. Tumor Response (mRECIST – CR, PR, SD, PD)
- c. Return to normal activities
- d. Pain VAS

14. Arteriovenous malformations:

- a. EQ-5D
- b. Return to normal activities
- c. Pain VAS

4 Study Design

This is a prospective, multi-center, registry study to assess the procedural success, technical success, and complication rate of radial access procedures using HydroPearl microspheres.

A subject is considered enrolled into the study once the guidewire is inserted into the radial artery.

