Procedural, access, closure evaluations		X				
QoL questionnaires and return to normal activities	X		X	X	X	
Concomitant Medications (Anticoagulation / Antiplatelets Only)	X	X	X	X		
Device Related Adverse Events		X	X	X	X	

F. List of Abbreviations and Definition of Terms

AE:	Adverse Event
AV:	Arteriovenous
BMI:	Body Mass Index
BPH:	Benign Prostatic Hyperplasia
CEC:	Clinical Events Committee
CFR:	Code of Federal Regulations
CIP:	Clinical Investigational Plan, also referred to as (study) protocol
CRO:	Clinical Research Organization
CTRA:	Clinical Trial Research Agreement
eCRF:	Electronic Case Report Form
EQ-5D:	EuroQol Group standardized measure with 5 dimensions
HIPAA:	Health Care Portability and Accountability Act
ICF:	Informed Consent Form
ICH:	International Conference on Harmonization
IFU:	Instructions for Use
IRB/EC:	Institutional Review Board/Ethics Committee
IPSS:	International Prostate Symptom Score
MI:	Myocardial Infarction
mRECIST:	Modified Response Evaluation Criteria in Solid Tumors
PAE:	Prostate Artery Embolization
PG:	Performance Goal
QoL:	Quality of Life
SAE:	Serious Adverse Event
SDV :	Source Document Verification
UADE:	Unanticipated Adverse Device Effect
UFE	Uterine Fibroid Embolization
UFS-QOL:	Uterine Fibroid Symptom Quality of Life Questionnaire
VAS	Visual Analog Scale

1 Background

The transradial approach to percutaneous interventions has generated intense interest over the past decades. Initially researched in the context of percutaneous coronary interventions (PCI), early reports of successful transradial access (TRA) included coronary angiography in 1989 (Campeau, 1989) and the first successful TRA coronary angioplasty and stent implantation in the years 1992 and 1993, respectively. (Kiemeneij & Laarman, 1993).

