Gjoreski, et al. (2019) directly compared the safety and feasibility of UFE when achieved through radial as opposed to femoral access. In this retrospective study, 13 femoral procedures and 11 transradial procedures all yielded a 100% success rate with no significant difference in access site related and overall adverse events noted between cohorts. Procedure and fluoroscopy times were reportedly shorter in the radial group; a mean procedure time of 60.3 minutes was associated with the radial group as compared to 72.4 minutes in the femoral cohort, and mean fluoroscopy time was 21.1 minutes and 25.3 minutes in the radial and femoral cohorts, respectively. (Gjoreski, Gjoreski, & Nancheva, 2019).

The development of transradial access for embolization of hepatic tumors can be traced back to a 2003 report by Shiozawa et al. (2003) which described transcatheter arterial chemoembolization (TACE) in 327 patients, 177 of which were accessed radially and 150 via femoral access. Therapeutic efficiency was observed in both cohorts, with a lower complication rate in the radial cohort (4.6%) compared to the femoral (12.7%). (Shiozawa, et al., 2003). In addition to chemoembolization, radial access has also been utilized for radioembolization of hepatic tumors. A study by Fischman, et al. published in 2016 described 30 procedures conducted in 26 patients which supported the safety and tolerability of TRA for hepatic artery embolization. In this study, 14 TACE procedures, 14 Y90 procedures and 2 bland embolization procedures yielded a 100% technical success rate with no major AEs reported at one month follow up. (Fischman, et al., 2013) . In a 318 patient study, a total of 329 planning angiograms and 245 Y90 embolization procedures resulted in technical success in 97.7% of cases, superficial bruising observed in 2.3% of cases, and a radial artery occlusion rate of 1.6%. (Bishay, et al., 2016) .

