The largest study involving safety and feasibility of transradial access for non-coronary interventions includes both UFE and hepatic artery embolization among other visceral interventions. In this single center study, 936 patients undergoing 1,512 consecutive TRA procedures were retrospectively analyzed. Of these procedures, UFE accounted for 116, and TACE, Y90 mapping and Y90 infusion accounted for 485, 391 and 293 procedures, respectively. Combined analysis indicated a technical success rate of 98.2%. Major complications, including one pseudoaneurysm and one seizure, were reported at 0.13%, and minor complications, including hematomas, RAO, RAS and arm pain, were observed in 2.38% of cases. Twenty-seven cases, representing 1.8%, required crossover to transfemoral access. The favorability of these results towards radial access led authors to pronounce TRA as a promising alternate primary access site in a variety of peripheral vascular interventions. (Posham, et al., 2016)

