7.2 Procedure

Subjects that meet the eligibility criteria and have signed the informed consent will have their scheduled procedure performed in accordance with investigator/site standard practices. Any on-label use of HydroPearl microspheres are permitted this study; that is, treatment of arteriovenous malformations and hypervascular tumors including uterine fibroids.

Table 2: Schedule of Events

Assessment	Screening / Baseline	Procedure	Discharge	30 Day Follow-up ±14 days	180 Day Follow-up ±30 days	365 Day Follow-up ±30 days
Informed Consent	X					
Eligibility Criteria	X					
Medical History/Demographics	X					
Pregnancy Test [¶]	X					
Blood Tests, including platelets and INR (if available) *	X	X	X	X	X	X
Embolized target organ Imaging (if available)	X	X	X	X	X	X
Physical Exam	X	X	X	X	X	X
Procedure, Access, Closure Evaluations		X				
Quality of Life questionnaires and return to normal activities	X		X	X	X	X
Concomitant Medications (Intra-op and Anticoagulation / Antiplatelets Only)	X	X	X	X		
Device Related Adverse Events ^{§§}		X	X	X	X	X

[¶] Pregnancy test if female of child-bearing potential (collected prior to procedure according to site standard of care)

* Blood Tests include Complete Blood Count (CBC), Platelet Count, Serum Creatinine, Hemoglobin (HGB), Blood Urea Nitrogen (BUN), Hematocrit (HCT) and Prothrombin time/INR, only as collected per standard of care

^{§§} Device related adverse events should be recorded during the entire course of the study from time of enrollment through end of 180 Day Follow-up visit.

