7.7 Clinical Data Collection

Information about subject demographics, eligibility requirements, procedure, specific concomitant medications as well as complications and/or device related adverse events will be collected on the eCRFs provided by the Sponsor. The eCRFs should accurately reflect data contained in the subject's medical records (i.e. source documents).

8 Adverse Events

Subject complications will be monitored via the reporting of device related adverse events occurring from the time of enrollment (insertion of guidewire into radial artery) through study completion (withdrawal for any reason or completion of 365-day follow-up visit). For this registry, adverse events collected will be limited to any events possibly, probably or definitely related to a Terumo device, as described below in Section 8.2.

Where an adverse event has, by its nature, a prolonged course, the event will be considered a single event and not multiple events.

The investigator is not required to actively seek adverse events from a subject once a subject has exited the study. If the investigator learns of any device related adverse event at

any time after a subject's exit from the study, the investigator should promptly report it to the Sponsor.

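### The minor access-site evaluation is headed as complications of radial artery occlusion and has no required post-procedure collection, so it is mislabelled and likely under-counted

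*Combined protocol and SAP*

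**What the plan says.** Section 3.2.2 item 1, and the synopsis in the same words, define an additional evaluation as "Incidence of Radial Artery Occlusion Complications at any time". Its five components are arteritis, cellulitis, ecchymosis, pain at the puncture site and hematoma.

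Occlusion appears elsewhere in its own right. Section 3.2.1 opens a primary safety list with "Radial Access related complications are defined as", and radial artery occlusion is the first entry. The Background (section 1) reports, for one large series, that "minor complications, including hematomas, RAO, RAS and arm pain, were observed in 2.38% of cases". For a radioembolization series it gives "superficial bruising observed in 2.3% of cases, and a radial artery occlusion rate of 1.6" per cent.

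On timing, Table 2 in section 7.2 has a row "Procedure, Access, Closure Evaluations", ticked at Procedure only. The synopsis schedule has the matching row "Procedural, access, closure evaluations", also ticked at Procedure only. Device related adverse events are ticked at Procedure, Discharge and every follow-up visit. The Table 2 footnote to that row sets the recording period as "from time of enrollment through end of 180 Day Follow-up visit", while section 8 runs it "through study completion (withdrawal for any reason or completion of 365-day follow-up visit".

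**The concern.** The stated objective includes complication rates with radial access, and this is the only item that gathers the minor puncture-site events as a group. Two things are unclear.

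- **Who counts.** The heading names complications of occlusion, but the components are general puncture-site events. Someone building the eCRF or programming the table could count a hematoma only when the radial artery is occluded, or could count it in everyone. The item states no numerator or denominator.
- **When it is looked for.** The item covers any time, yet no schedule row names these events and no visit after the procedure requires the puncture site to be examined. An event that nobody was asked to record cannot be told apart from no event.

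At stake is a descriptive rate that readers will take as the minor access-site complication rate of the registry.

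**Working it through.** **Does the heading fit its list?**

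- Section 3.2.1 makes occlusion one component of access complications, not the parent category.
- The large Background series places hematoma and occlusion side by side as minor complications.
- The radioembolization series gives bruising at 2.3% and occlusion at 1.6%. If both rates share a denominator (assumption), at least 2.3 − 1.6 = 0.7 bruising cases per 100 had no occlusion. Bruising is therefore not a subset of occlusion.

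The heading contradicts the protocol's own use of the terms.

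**Where can the five events be recorded after the procedure?**

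- *Procedure/access/closure row:* Procedure only. Its name matches the three separate endpoint groups for procedure, access and closure (3.2.2 items 4 to 6), so it is probably not the row for item 1.
- *Device related adverse event row:* ticked at all visits from Procedure on, but section 8 restricts collection to events with at least a possible relation to a Terumo device. The row is ticked at 365 days, its footnote stops at 180 days, and section 8 continues to 365 days.
- *Physical exam row:* ticked at Discharge and follow-up. Sections 7.6.2 and 7.6.3 require only the quality of life questionnaire at 30 and 180 days, and section 7.6.4 allows a telephone contact at 365 days. Nothing directs the exam to the puncture site.
- *Section 7.7:* complications go on the eCRF, with no visit and no list of events.
- *Section 13.5:* only observed cases are analysed. The plan does not say whether a subject with no access-site record is event-free or missing.

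**Arithmetic.** The plan gives no expected rate for this item. Its one stated probability (section 13.1) concerns major complications and reproduces: 1 − (1 − 0.016)^100 = 0.8007, that is, above 80%.

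The figures below are illustrations for N = 100 that borrow Background rates. Those are rates per case in other series. The 2.38% also includes occlusion and spasm, so it is not a rate for these five events.

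- *Heading taken literally, occlusion 1.6%:* expected occluded subjects = 100 × 0.016 = 1.6. P(none) = 0.984^100 = 0.199. The rate could not exceed about 1.6%.
- *All subjects, 2.38%:* expected = 2.38. P(at least one) = 1 − 0.9762^100 = 0.910.
- *All subjects, 2.38%, with only a share f of events recorded (f is an assumption):*

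| f | Expected recorded, 100 × 0.0238 × f | P(at least one), 1 − (1 − 0.0238f)^100 |
|---|---|---|
| 0.25 | 0.60 | 0.449 |
| 0.50 | 1.19 | 0.698 |
| 0.75 | 1.79 | 0.835 |
| 1.00 | 2.38 | 0.910 |

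The documents give no basis for choosing f.

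**The case against.** The best defence is that only the label is wrong. The five events are named one by one, so a site recording a hematoma need infer nothing from the heading. Section 13.3 bases the analyses on all enrolled and treated subjects, and nothing expressly restricts item 1 to occluded subjects. Counted that way, the heading does not distort the figures. This stands. A reader might infer that the rate must be wrong on any reading, but the documents do not support that. The literal-reading figures above show what the wording permits, not what is likely to happen.

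A reader might also infer from the Procedure-only tick that these events are never looked for after the procedure. That goes too far as well. The row most naturally belongs to the procedural, access and closure endpoints, and other routes exist. The adverse event route has a low threshold: section 8.4 rates as possible even an event thought unlikely to be caused by the device, and the restriction covers any Terumo device, not only the microspheres.

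These routes narrow the gap without closing it. A puncture-site event judged unrelated to any Terumo device falls outside adverse event collection, and neither the exam nor section 7.7 supplies a required check. How late these events tend to appear is not stated in the documents, and the point does not depend on it, because the item itself claims to cover any time.

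**Conclusion.** The point holds in a limited form. The heading is wrong in both places where it appears and leaves room for a count confined to occluded subjects. Separately, the plan has no required, relatedness-neutral collection of these events after the procedure, so the rate is likely to be under-counted even when read sensibly. That direction assumes that some such events arise after the procedure and are judged unrelated to a Terumo device, or are not looked for. The size cannot be calculated from the documents.

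The effect is confined to an additional, descriptive evaluation with no hypothesis test. The primary safety list in section 3.2.1 is correctly headed and is untouched by this wording.

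**What to change.** 1. In the synopsis and section 3.2.2 item 1, retitle the item *Incidence of minor radial access-site complications*. Define it as subjects with at least one of the five events among all subjects in the Primary Analysis Set, regardless of radial artery occlusion.
2. Add a yes/no access-site item for the five events to the eCRF and both schedules at Procedure, Discharge and 30 days, recorded regardless of device relatedness. A recorded no then separates event-free subjects from missing ones.
3. Either extend that item to 180 and 365 days, or replace the any-time wording with the period actually collected.
4. Reconcile the 180-day footnote in Table 2 with the 365-day period in section 8.

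The cost is a protocol wording change and a short eCRF item at existing visits, with no new visit. The reported minor complication rate may come out higher.

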	
e. Qmaxf. Prostate volume6. Liver Tumor Embolization:
a. Tumor response (CR, PR, SD, PD)b. EQ-5Dc. Return to normal activitiesd. Pain VASe. Disease stage7. Other Hypervascular tumors
a. Infarctionb. Return to normal activitiesc. Pain VAS8. Arteriovenous malformations:
a. EQ-5Db. Return to normal activitiesc. Pain VAS
Inclusion Criteria	
1. Subject is \geq 18 years old2. Subject is scheduled for an embolization procedure for treatment with HydroPearl microspheres via radial access.3. Subject is willing and able to complete follow-up requirements4. Subject is willing and able to sign a written Informed Consent form prior participating in the registry.
Exclusion Criteria	
1. Unable to have a procedure with radial access for any reason.2. Participating in another clinical study which, in the opinion of the investigator, could impact the results of this registry.3. Pregnant or planning to become pregnant during the study.
Statistical Analysis	
Endpoints will be reported with descriptive statistics as well Kaplan-Meier survival curves where appropriate.
 
Sub-group analyses include, but are not limited to:
 
• UFE procedure• PAE procedure• Liver embolization procedure• Other hypervascular tumors procedure• AVM embolization procedures
Imaging Assessments	Imaging datasets will be conducted for baseline, procedure, and follow-ups per site standard of care and results entered into eCRF. Images will not be collected or archived by the Sponsor.
Safety	The Principal Investigator at each site will be responsible for reviewing and following any adverse events per site standard of care.
Data Quality	Electronic case report forms will be used to collect data evaluations in this registry.

	Source data verification will be completed during periodic on-site monitoring visits. The frequency of on-site visits will be specified in the study monitoring plan.					
Schedule of Events						
Assessment	Screening / Baseline	Procedure	Discharge	30 Day Follow-up ±14 days	180 Day and 365 Day Follow-ups ±30 days	
Informed Consent	X					
Eligibility Criteria	X					
Medical History/Demographics	X					
Pregnancy Test	X					
Blood Tests (if available)	X	X	X	X	X	
Imaging (if available)	X	X	X	X	X	
Physical Exam	X		X	X	X	

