7.6.1 Discharge Visit

The subject may be discharged when clinically stable, at the discretion of the investigator.

7.6.2 30 Day Visit (\pm 14 days)

All study sites will be asked to collect follow-up data per each subject at 30 days post-procedure. Study reported evaluations are not required except for the quality of life questionnaire; otherwise all data collected will be per standard of care. A typical follow-up visit may include blood tests, imaging, physical exam, review of concomitant medications and any device related adverse events.

7.6.3 180 Day Visit (\pm 30 days)

All study sites will be asked to collect follow-up data for each subject at 180 days post-procedure, per site standard of care. Study reported evaluations are not required except for the quality of life questionnaire; otherwise all data collected will be per standard of care. A typical follow-up visit may include blood tests, imaging, physical exam, review of concomitant medications and any device related adverse events.

7.6.4 365 Day Visit (\pm 60 days)

All study sites will be asked to collect follow-up data via telephone or visit for each subject at 365 days post-procedure. If a clinic visit is standard of care at 365 days, data from the visit will be collected. If a clinic visit is not standard of care, follow-up information for this visit will be collected via telephone. This 365-day visit will conclude the subject's participation in the study.

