9.2 Potential Benefits

Subjects enrolled in this clinical study will be monitored closely throughout the study and have regular assessments according to the investigator's standards of care. The data collected during the clinical study will provide further understanding of procedural and technical success of radial access for HydroPearl procedures.

10 Monitoring

Data will be collected using eCRFs for this study. Sites will enter data directly into the eCRFs via a web-based system. Sponsor representatives (study monitors) will schedule periodic, on-site visits to review source data and compare to eCRFs.

Study monitors will work in accordance with Sponsor standard operating procedures (SOPs) and the Study Monitoring Plan.

At the site, monitors will perform and verify the following:

- The adequacy and experience of the study center including Sponsor notification of any problems relating to facilities, technical equipment or medical staff
- Written Informed Consent has been obtained from all subjects prior to any study related procedures being performed and that data is recorded correctly and completely
- Source Document Verification (SDV): comparing data in the eCRFs to ensure they correspond with applicable source data, and to inform the Sponsor and investigator of any discrepancies, errors or omissions
- Ensure adherence to the protocol and applicable regulations at the site and notify the Sponsor promptly of any deviations
- Evaluate subject compliance and support subject retention efforts at the site

11 Image Analysis

Imaging, if completed, will be analyzed per standard of care at each site and results reported in eCRF; however, images will not be collected nor archived by the Sponsor.

12 Device Failure and Malfunction

A device failure has occurred when the device is used in accordance with the IFU, but does not perform as described in the IFU, and negatively impacts treatment of the study subject.

13 Statistical Methods

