13.5 Handling of Missing Data

All data will be collected when possible to limit the amount of missing data. Site study coordinators will work with the site principal investigator to collect accurate patient data. The number of missing data will be reported. Only observed cases will be considered.

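### Imaging results labelled as HydroPearl effectiveness come only from subjects who happened to be scanned, and the plan neither asks why a scan was done nor compares scanned with unscanned subjects

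*Combined protocol and SAP*

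**What the plan says.** Follow-up imaging is left to each site throughout. The synopsis states: "Imaging datasets will be conducted for baseline, procedure, and follow-ups per site standard of care and results entered into eCRF". The imaging row of Table 2 in section 7.2 is worded "Embolized target organ Imaging (if available", and this condition applies at every visit. Sections 7.6.2 and 7.6.3 say of the 30-day and 180-day visits: "Study reported evaluations are not required except for the quality of life questionnaire; otherwise all data collected will be per standard of care". Section 7.6.4 says of day 365: "If a clinic visit is not standard of care, follow-up information for this visit will be collected via telephone". Under section 11, "Imaging, if completed, will be analyzed per standard of care at each site and results reported in eCRF", and the sponsor keeps no images.

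Section 3.2.2 (item 10, UFE) makes the MRI result conditional: "If post-op MRI is obtained per standard of care: Effectiveness of HydroPearl measured by MRI". Infarction category, uterine volume and dominant fibroid volume sit under that line. Prostate volume, infarction in other hypervascular tumors, and mRECIST response carry neither the condition nor the label. For them the optional status follows from the synopsis, Table 2 and section 11.

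On analysis, section 13.5 promises a count of missing values and then says "Only observed cases will be considered". Section 13.2.2 assigns results to the visit named in the eCRF. Section 13.4 examines differences between sites for the primary evaluations only.

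**The concern.** Leaving imaging to routine care is a reasonable choice for a registry. The difficulty lies in what is then done with the images. One site may scan every woman at six months, while another scans only those whose bleeding persists. Both practices can be called standard of care, so that phrase does not separate them. Under an observed-case analysis the two kinds of scan enter one summary within the procedure group, and for UFE that summary is called the effectiveness of the product.

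The planned 95% confidence intervals (section 13.2) describe sampling error and would not show this selection. The missing-value count says how many results are absent, not why. Because the UFE item applies only when an MRI exists, it is not even clear that an unscanned woman would be counted as missing.

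At stake is whether the infarction, volume and response figures can be read as describing treated subjects. This matters more than it otherwise would because section 1.2 states that no clinical study of HydroPearl has been published, and section 2.1 gives recording real-world efficacy as a purpose of the registry.

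**Working it through.** **The plan's own figure.** The only sample-size calculation is in section 13.1: more than an 80% chance of seeing at least one major complication among 100 evaluable patients at a rate of 1.6%. It reproduces: 1 − 0.984^100 = 0.8007. It concerns complications and has no bearing on imaging. The documents give no figure for the share imaged, the reasons for scanning, or the expected response, so everything below rests on assumed inputs.

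**Formula.** Let P be the true response rate among treated subjects, and let a and b be the probabilities that a responder and a non-responder are imaged. The observed-case rate is

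P·a / [P·a + (1 − P)·b].

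When a = b this equals P. Only the ratio of a to b matters for the bias.

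**Results for P = 80% (assumed).**

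| a | b | Calculation | Observed | Difference (points) |
|---|---|---|---|---|
| 0.50 | 0.50 | 0.40 / 0.50 | 80.0% | 0 |
| 0.50 | 0.75 | 0.40 / 0.55 | 72.7% | −7.3 |
| 0.40 | 0.80 | 0.32 / 0.48 | 66.7% | −13.3 |
| 0.75 | 0.50 | 0.60 / 0.70 | 85.7% | +5.7 |
| 0.80 | 0.40 | 0.64 / 0.72 | 88.9% | +8.9 |

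For the same four unequal pairs, a true rate of 60% gives observed rates from 42.9% to 75.0%, and a true rate of 90% gives 81.8% to 94.7%.

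**Bounds with no assumption about why scans were done.** If a share m of treated subjects is imaged and the observed rate is r, the rate among all treated subjects lies between r·m (every unscanned subject a non-responder) and r·m + (1 − m) (every one a responder). With r = 80%:

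- m = 90%: 72% to 82%
- m = 75%: 60% to 85%
- m = 50%: 40% to 90%
- m = 30%: 24% to 94%

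These are limits, not likely values. They show that the number imaged over the number treated is the first figure a reader needs.

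**Limit of the illustration.** The plan defines no binary imaging success. Infarction has four categories, mRECIST has four, and volumes are continuous. The same reweighting acts on each category share or mean, but the percentages above apply only to a dichotomy.

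**The case against.** The case on the other side is substantial, and much of it stands.

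- A reader might infer that the imaging rates are biased. The documents do not show this. No section says that any site scans only symptomatic patients, and if scanning is unrelated to outcome the bias is zero.
- A reader might infer that the reason for a scan will go unrecorded. The eCRF is not among the documents, and section 7.7 describes its contents only in general terms. What can be said is that the protocol does not ask for this item.
- A reader might take the imaging results to be the registry's only objective efficacy data. They are not. Qmax is listed for prostate embolization, and procedural and technical success (section 3.2.1) need no follow-up scan.
- A reader might conclude that the direction of any bias could never be judged from the database. That goes too far. Table 2 schedules quality-of-life questionnaires at baseline and every follow-up, and section 3.2.2 lists UFS-QoL, bleeding and bulk symptoms, IPSS and EQ-5D. These would allow imaged and non-imaged subjects to be compared. The plan simply does not specify that comparison.
- Much larger distortions can be produced. With a true rate of 80%, scanning every failure but only a fifth of successes gives 0.16 / (0.16 + 0.20) = 44%. Nothing in the documents supports so extreme a pattern.
- These are descriptive additional evaluations, with no hypothesis test (sections 13.1 and 13.7), and the effectiveness label is attached to UFE MRI alone.

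These arguments lower the severity and rule out the stronger claims. They leave the gap in place: the plan as written mixes scans of different origin, examines no site differences for these items, and provides nothing to show whether selection occurred.

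**Conclusion.** The concern holds in a limited form. Follow-up imaging is optional, only observed cases are analysed, and the protocol specifies neither a record of scan indication nor a comparison of imaged with non-imaged subjects. The imaging results may therefore misstate response among treated subjects, in either direction, if being scanned depends on outcome.

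The size is unknown. The range of about 67% to 89% around a true 80% rests on an assumed 1.5- to 2-fold difference in imaging probability and on a binary response that the plan does not define. Severity is minor to moderate: the primary evaluations are unaffected, but as planned the imaging figures support statements about imaged subjects only.

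**What to change.** Amend sections 3.2.2 and 13.5, and the eCRF if it lacks the field:

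1. With each follow-up image and its date, record whether it was routine at that site or prompted by symptoms or suspected failure.
2. Report the number imaged over the number treated, by procedure type, visit and site.
3. Show imaging results for routine and prompted scans separately as well as together.
4. Compare baseline features and the quality-of-life and symptom scores already collected (UFS-QoL, IPSS, EQ-5D) between imaged and non-imaged subjects. Section 3.2.2 lists no EQ-5D for other hypervascular tumors; pain VAS and return to normal activities can serve there.
5. Describe the results as applying to imaged subjects, not as the effectiveness of HydroPearl in all treated subjects.

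Step 4 is needed alongside steps 1 and 3. If satisfied patients are the ones who come back, their scans would be coded routine and the indication field would miss the selection.

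The cost is one eCRF field, a few extra tables, and smaller cells within procedure groups drawn from at most 100 subjects. Site imaging practice and patient burden do not change. The indication is best captured when the result is entered, since the sponsor holds no images to return to.
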